## 4.5. Safety Variables

Patient safety will be assessed through the collection of reported adverse events (AEs), clinical laboratory data, vital signs, ECG, Survey of Autonomic Symptoms Questionnaire, neurological exams and physical exams. Unless otherwise noted, the baseline value is defined as the last available value before the first dose of study drug.

Adverse events (AE) and Serious Adverse Events (SAE) will be collected from the time of informed consent signature and then at each visit until the End of Follow-up Clinic Visit. All AEs are to be coded to a “Preferred Term (PT)” and associated primary “System Organ Class SOC” according to the MedDRA® (the latest current available version).

An Adverse Event is any untoward medical occurrence in a patient or clinical investigation patient administered a pharmaceutical product and which does not necessarily have a causal relationship with this treatment.

A Serious Adverse Event is an adverse event (AE) that is classified as serious according to the criteria specified in the protocol.

Laboratory results, vital signs, or ECG abnormalities are to be recorded as AEs if they are medically relevant: symptomatic, requiring corrective therapy, leading to treatment discontinuation and/or fulfilling a seriousness criterion.

### 4.5.1. Safety Variables

The safety endpoints in the study are:

- Incidence of Adjudicated Arthropathy (AA) (as confirmed by an independent adjudication committee)
- Incidence of Destructive Arthropathy (DA) (as confirmed by an independent adjudication committee)
- Incidence of treatment-emergent adverse event (TEAEs)
- Incidence of SNS dysfunction (as diagnosed after consultation with an appropriate specialist, such as a neurologist and/or cardiologist)
- Incidence of peripheral sensory AEs that require a neurology consultation
- Incidence of all-cause joint replacement (JR) surgeries through week 16 and through the end of follow-up period (week 36)
- Incidence of JRs at telephone survey approximately 52 weeks after last dose of study drug

The raw incidence rate is defined as the number of events divided by the duration of the observation period and presented as number of events per 100 patient-years.

Additional safety endpoints that may be evaluated include:

- Survey of Autonomic Symptom scores from baseline to week 16 and from baseline to week 36

#### 4.5.2. Adverse Events of Special Interest

An AESI (serious or non-serious) is one of scientific and medical concern specific to the sponsor's product or program, for which ongoing monitoring and rapid communication by the investigator to the sponsor can be appropriate.

AESI are selected using e-CRF specific tick box on the AE page.

Events considered to be AESIs for the study are:

- Adjudicated arthropathy (as confirmed by adjudication)
- Sympathetic nervous system dysfunction (as diagnosed after consultation with an appropriate specialist, such as a neurologist and/or cardiologist)
- Peripheral sensory AEs that require a neurology or other specialty consultation
- JR surgery (AESI defined in Protocol Section 9.6.1.4 as elective JR surgery not due to new or worsening disease)

#### 4.5.3. Laboratory Safety Variables

The clinical laboratory tests include blood chemistry, hematology, urinalysis, urine chemistries, hs-CRP, and others. Samples for laboratory testing will be collected at the time points specified in the Schedule of Events ([Appendix 11.1](#)). Clinical laboratory values will be in standard international (SI) units, including associated normal ranges provided by the central laboratory, and grouped by function in summary tables. Clinical laboratory values in conventional (US) units will also be available in the database, with associated normal ranges.

Both actual test values and "change from baseline" values (defined as the post-baseline value minus the baseline value) will be used in central lab result summaries. Potentially clinically significant values (PCSV) ranges will be applied to central lab test values as applicable (see [Appendix 11.2](#) for PCSV definitions).

#### 4.5.4. Biomarker variables

Biomarker analysis will be performed in a separate biomarker SAP.

#### 4.5.5. Vital Signs

Vital Sign parameters include:

- Body temperature (°C)
- Supine/standing/orthostatic systolic and diastolic blood pressures (mmHg) and pulse (bpm)
- Respiratory rate (bpm)

Both actual values and "change from baseline" values (defined as the post-baseline value minus the baseline value) will be used in the result summaries. Potentially clinically significant values (PCSV) ranges will be applied to the vital sign parameter values as applicable (see [Appendix 11.2](#) for PCSV definitions).

#### 4.5.6. Orthostatic Hypotension

A patient will be determined to have orthostatic hypotension if any of the following criteria are met:

- If the supine blood pressure is <160 mmHg systolic, a decrease in either the 1 or 3-minute standing systolic blood pressure of  $\geq 20$  mmHg or a decrease in the standing diastolic blood pressure of  $\geq 10$  mmHg from the supine systolic or diastolic blood pressure

OR

- If the supine blood pressure is  $\geq 160$  mmHg systolic, a decrease in either the 1 or 3-minute standing systolic blood pressure of  $\geq 30$  mmHg or a decrease in the standing diastolic blood pressure of  $\geq 15$  mmHg from the supine systolic or diastolic blood pressure

OR

- An increase in either the 1 or 3-minute standing heart rate of  $\geq 30$  bpm from the supine heart rate

OR

- The patient is unable to stand for either one of the standing blood pressure measurements due to dizziness or lightheadedness

Confirmed orthostatic hypotension is defined as initial assessment meeting the above orthostatic hypotension criteria confirmed by subsequent repeated assessments per protocol or if initial assessment met the above orthostatic hypotension criteria yet repeated assessments were not performed.

#### 4.5.7. 12-Lead Electrocardiography

Standard 12-lead ECG parameters include P-R interval, QT interval, QTc interval including QTcF and QTcB, QRS interval, ventricular rate and heart rate.

QTcF and QTcB corrections are defined as follows:

QTcF and QTcB are defined as follows:

$$\text{QTcF (ms)} = \text{QT} / \text{RR}^{1/3} \text{ and } \text{QTcB (ms)} = \text{QT} / \text{RR}^{1/2},$$

where QT is the uncorrected QT interval measured in ms, and RR is 60/HR with HR being the heart rate in beats per minute.

Potentially clinically significant values (PCSV) ranges will be applied to the ECG parameter values as applicable (see [Appendix 11.2](#) for PCSV definitions).

#### 4.5.8. Physical and Neurological Examination Variables

Physical examination assessments will be described as normal or abnormal for each body system examined. Neurological evaluations of specific domains as listed in the protocol will be described as normal or abnormal.

#### 4.5.9. Other Safety Variables

- Joint Pain Questionnaire:
  - Number of subjects with significantly worse joint pain in any joint at each scheduled visit
  - Number of subjects with significantly worse joint pain by joint at each scheduled visit
- Joint space width for specified joints at each scheduled visit.
- Joint replacement:
  - number and percentage of patients with joint replacement (all JRs)

#### 4.6. Pharmacokinetic Variables

The Pharmacokinetic (PK) variable will be fasinumab concentrations in serum at specified sampling time points.

#### 4.7. Anti-Drug Antibody Variables

Samples for Anti-Drug Antibody (ADA) evaluation will be collected at baseline and at subsequent study visits.

Anti-drug antibody variables will include ADA status (positive or negative) and titer as follows:

- Total subjects negative in the ADA assay at all time points analyzed
- Pre-existing immunoreactivity - a positive ADA response at baseline with all post-dose ADA results negative, or a positive ADA response at baseline with all post-dose ADA responses less than 9-fold over baseline titer levels.
- Treatment emergent - defined as any post-dose positive ADA response when baseline results are negative
  - Persistent - A positive result in the ADA assay detected in at least 2 consecutive post baseline samples separated by at least a 16-week post baseline period [based on nominal sampling time], with no ADA-negative results in-between, regardless of any missing samples
  - Indeterminate - A positive result in the ADA assay at the last collection time point analyzed only, regardless of any missing samples
  - Transient - Not persistent or indeterminate regardless of any missing samples
- Treatment boosted - defined as any post-dose positive ADA response that is at least 9-fold over the baseline level when baseline is positive in the ADA assay
- Titer Values
- Titer category: low (titer <1,000); moderate (1,000 ≤ titer ≤ 10,000); high (titer >10,000)
- Neutralizing ADA activity for samples positive in the ADA assay

## 5. STATISTICAL METHODS

For continuous variables, descriptive statistics will include the following: the number of patients reflected in the calculation (n), mean, median, standard deviation (SD), minimum, maximum, and the first and third quartiles (Q1 and Q3).

For categorical or ordinal data, frequencies and percentages will be displayed for each category.

### 5.1. Demographics and Baseline Characteristics

Demographic and baseline characteristics will be descriptively summarized by treatment group and overall based on the FAS. Parameters to be summarized include those described in Section 4.1.

### 5.2. Medical History

Medical history will be descriptively summarized by treatment group and overall for the FAS. Summaries will show patient counts (percentages) by primary SOC and PT. The tables will be sorted by decreasing frequency of primary SOC in the fasinumab group. Within each primary SOC, PTs will be sorted by decreasing frequency in the fasinumab group.

### 5.3. Prior and Concomitant Medications

#### Prior Medications

All prior medications, dictionary coded by WHO, will be descriptively summarized by treatment group based on the FAS. Summaries will present patient counts (and percentages) for all prior medications, by decreasing frequency of the fasinumab group incidence of ATC followed by ATC level 2, ATC level 4 and preferred term. In case of equal frequency across anatomic or therapeutic categories, alphabetical order will be used. Patients will be counted once in each ATC category (anatomic or therapeutic) linked to the medication but may be counted several times for the same medication.

#### Concomitant Medications

All concomitant medications, dictionary coded by WHO, will be descriptively summarized by treatment group based on the SAF. Summaries will present patient counts (and percentages) for the concomitant medication groups described in Section 4.3 for all concomitant medications, by decreasing frequency of the fasinumab group incidence of ATC followed by ATC level 2, ATC level 4 and preferred term. In case of equal frequency across anatomic or therapeutic categories, alphabetical order will be used. Patients will be counted once in each ATC category (anatomic or therapeutic) linked to the medication, hence may be counted several times for the same medication.

The following will be summarized:

- Prior Medications
- Concomitant medications
- Post-treatment medications

- On-study (Concomitant + Post-Treatment) Medications

When medication start/end date is missing, the rules for determining whether a medication is prior, concomitant, or post-treatment, are specified in Section 6.3.

#### **5.4. Prohibited Medications**

Number and percentage of patients with prohibited medications will be descriptively summarized by treatment group based on the SAF. The tables will be sorted by decreasing frequency of ATC Level 2, ATC Level 4, and preferred term in the fasinumab group.

The number of patients with NSAID use during the treatment period will be summarized by treatment group based on the SAF.

Total NSAIDs-use days during the treatment period and within 16 weeks after last study drug administration (before AA for patients with AA) will be summarized by treatment group for patients in the SAF.

#### **5.5. Patient Disposition**

The disposition of patients in the study will be summarized by treatment group and overall for FAS.

##### **5.5.1. Screening Disposition**

Percentages will be calculated using the number of screened patients as the denominator.

- Screened patients (defined as having signed the ICF).
- Patients randomized (defined in the protocol as having received a randomization number per IVRS).
- Patients did not meet inclusion/exclusion criteria but randomized (if applicable).
- Patients treated but not randomized (if applicable).
- Screen Fail patients. Reason for screen failure will be provided.

Additionally, the following listings will be provided (if applicable):

- Listing of Patients Treated but not Randomized.
- Listing of Screening Failures and reasons for all screen failed patients.

##### **5.5.2. Treatment and Study Disposition**

Unless otherwise noted, percentages will be calculated using the number of patients in FAS as the denominator. This will be summarized by treatment group and overall for the study. Summaries will provide the frequency (and percentage as applicable) of patients that met the criteria for the following variables:

- Patients randomized (defined as having received a randomization number). This row will reflect grouping based on randomization assignment.

- Patients randomized but not treated. This row will reflect grouping based on randomization assignment.
- Patients randomized and treated.
- Patients who completed study treatment, patients who discontinued treatment and reason for treatment discontinuation.
- Patients who completed the study, patients who withdrew from the study and reason for study withdrawal.

Additionally, the following listings will be provided (if applicable):

- Listing of Patients Randomized but not Treated.
- Listing of Patients Randomized but not Treated with the Randomized treatment.
- Listing of Patient Disposition for all Randomized Patients.

### 5.5.3. Analysis Set

Summary of the number (and percentage) of patients in each analysis set will be presented by treatment group and overall.

## 5.6. Extent of Study Treatment Exposure and Compliance

The analysis population is based on the SAF.

### 5.6.1. Measurement of Treatment Compliance

Compliance with protocol-defined investigational product will be calculated by treatment group as follows:

$$\frac{\text{Number of actual injections of study drug received during the treatment exposure period}}{\text{Number of planned injections of study drug during the treatment exposure period on or before the time that the patient discontinued from the treatment phase of the study}} \times 100$$

Treatment compliance will be presented by the descriptive statistics and the number (%) of patients who have 1, 2, 3, and 4 SC injections will be displayed.

### 5.6.2. Exposure to Investigational Product

The duration of treatment exposure to fasinumab and placebo SC doses will be calculated as:

- (Date of last dose of study drug– date of first dose of study drug) + 28

The duration of exposure will be summarized for each treatment group using the number of patients (n), mean, standard deviation, median, Q1, Q3, minimum, and maximum.

The number (%) of patients with exposure duration periods will be presented by specific time periods. The time periods of interest are specified as:  $\geq 1$  day,  $\geq 29$  days,  $\geq 57$  days,  $\geq 85$  days, and  $\geq 113$  days.

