5. STUDY DESIGN

5.1. Study Description and Duration

This is a phase 3, randomized, double-blind, placebo-controlled, parallel-group study to evaluate the efficacy and safety of fasinumab in patients with moderate-to-severe non-radicular CLBP who have radiographically confirmed OA of the knee or hip, and who have a history of inadequate relief of their CLBP or intolerance to current analgesic therapy and inadequate relief of their CLBP from non-pharmacologic therapy. The study consists of a screening period of up to 30 days, a 7 (+3 day)-day pre-randomization period during which all pain medication except study-provided rescue medication will be discontinued, a 16-week treatment period (with the last Q4W dose of study drug administered at week 12), a 20-week follow-up period, and a final phone contact approximately 52 weeks after the last dose of study drug is administered ([Figure 1](#)).

Figure 1: Study Flow Diagram

EOS- End of study

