7. STUDY TREATMENTS

7.1. Investigational Treatment

Fasinumab drug product is supplied for this study in 1 mL single-use pre-filled syringes that deliver 0.5 mL of 6 mg/mL solution to provide a single 3 mg dose of study drug.

All patients will receive SC injections of fasinumab or fasinumab-matching placebo. Patients will be randomized to 2 treatment arms in a 1:1 ratio to receive either fasinumab 3 mg SC Q4W or fasinumab-matching placebo SC Q4W. All SC injections will be in the abdomen, thigh, or upper arm. Instructions for dose preparation and study drug administration are provided in the pharmacy manual.

Doses of study drug must be given within ± 7 days from the scheduled dose date. If the window is missed, the dose should not be administered. The next dose should be administered at the next scheduled dosing date.

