10.4.4.3. Treatment Exposure

Because of the half-life of the biologic being studied, the duration of fasinumab exposure during the study will be presented by treatment group and calculated as:

(Date of last administration of study drug - date of the first study drug administration after randomization) + 28

The number and percentage of patients randomized and exposed to double-blind study drug will be presented by specific time period for each treatment group. The time periods of interest will be specified in the SAP.

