### 5.6.3. Length of Study Observation

The length of the observation period (days) will be calculated as:

- (Date of last study visit [up to End of Follow-up Clinic Visit] – date of first study drug dose) +1.

The observation duration will be summarized for each treatment group using the number of patients (n), mean, standard deviation, median, Q1, Q3, minimum, and maximum.

The number (%) of patients with observation periods will be presented by specific time periods. The time periods of interest are specified as:  $\geq 1$  day,  $\geq 29$  days,  $\geq 57$  days,  $\geq 85$  days,  $\geq 113$  days,  $\geq 141$  days,  $\geq 169$  days,  $\geq 197$  days,  $\geq 225$  days,  $\geq 253$  days, and  $\geq 449$  days

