## **5.9. Analysis of Safety Data**

The analysis of safety and tolerability will be performed on the SAF, as defined in Section 3.2.

The safety analysis will be based on the reported AEs and other safety information (clinical laboratory evaluations, vital signs, 12-lead ECG, Physical Examination, etc.).

Treatment-Emergent Potential Clinically Significant Values (PCSV) in laboratory variables, vital signs and ECG are defined in Appendix 11.2.

**Period of observation:** The observation period will be divided into three segments: pre-treatment, on-treatment and post-treatment.

- The pre-treatment period is defined as the time between when the patients give informed consent and the start of study drug.
- The on-treatment period is defined as the time from first dose of study drug up to 28 days after the last dose of study drug.
- The post-treatment period is defined as the time starting 29 days after last dose of study drug (after the on-treatment period) to up to 24 weeks post the last dose of study drug (up to week 36).

Day 1 is the first day of study drug, Day -1 is the day before Day 1, and there is no Day 0.

The time interval to detect any on-treatment event or abnormality is between the first dose of double-blind study drug injection and the end of treatment plus 28 days. Data collected outside this interval will be excluded from the on-treatment estimation of descriptive statistics and identification of abnormalities for laboratory evaluations, ECGs and vital signs. All post-baseline data during the interval will be used in the PCSV analysis including scheduled and unscheduled assessments.

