**Table 1: Visit Windows**

Visit No.	Visit	Targeted Study Days*	Analysis Window in Study Days
1	Screening	Day -30 to Day -11	$\geq -30$ and $\leq -11$
2	Pre-randomization Phone Call	Day -10 to -7	-10 to -1
3	Baseline #	1	1
4	Week 1	8	[2, 11]
5	Week 2	15	[12,20]
6	Week 4	29	[21,43]
7	Week 8	57	[44,71]
8	Week 12	85	[72,99]
9	Week 16	113	[100,127]
10	Week 20	141	[128,155]
11	Week 24	169	[156,183]
12	Week 28	197	[184,211]
13	Week 32	225	[212,239]
14	Week 36	253	[240,267]
15	Week 64	449	[436,456+]

\*Study days are calculated from the first dose of study drug (Day 1).

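### The top exposure row in SAP 5.6.2 (≥113 days) leaves out the patient given all four doses on schedule, who has 112 days under the + 28 formula.

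*SAP*

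**What the plan says.** SAP 5.6.2 defines the duration of exposure as the date of last dose minus the "date of first dose of study drug) + 28". Protocol 10.4.4.3 gives the same rule: "Date of last administration of study drug - date of the first study drug administration after randomization) + 28". The protocol leaves the time periods for tabulation to the SAP, and SAP 5.6.2 supplies them: "The number (%) of patients with exposure duration periods will be presented by specific time periods", namely ≥1, ≥29, ≥57, ≥85 and ≥113 days.

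Treatment lasts 16 weeks, "with the last Q4W dose of study drug administered at week 12". The schedule of events puts the injections at baseline and weeks 4, 8 and 12, that is Days 1, 29, 57 and 85, and the week 16 visit on Day 113. Protocol 7.1 adds: "Doses of study drug must be given within ± 7 days from the scheduled dose date".

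Two neighbouring SAP sections count days differently. In 5.6.3 the length of observation is the date of last visit minus the "date of first study drug dose) +1", tabulated at the same cut-points and several later ones. In 5.9 the on-treatment period is the "time from first dose of study drug up to 28 days after the last dose of study drug".

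**The concern.** The cut-points 29, 57, 85 and 113 are the target study days of the week 4, 8, 12 and 16 visits. A study-day number counts the first day as 1, so it suits an inclusive count. The exposure formula takes a plain difference of dates and adds 28, so on-schedule exposures come out as multiples of 28. A cut-point that is one more than a multiple of 28 then lies just above the on-schedule value.

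This matters most at the top. Someone reading the table could well take ≥113 days as 16 weeks of exposure and read a low or zero count as few patients having had the full course. Under the stated formula, the patient treated exactly as planned for 16 weeks is not in that row.

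**Working it through.** **Inputs.** Exposure formula: SAP 5.6.2 and protocol 10.4.4.3. Target dose days 1, 29, 57 and 85: schedule of events. First dose is Day 1: footnote to SAP Table 1. Dosing window ±7 days: protocol 7.1.

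**Where 113 does fit.**
- SAP 5.6.3, visit on Day 113: (113 − 1) + 1 = 113.
- SAP 5.9, last day of the on-treatment period after a Day 85 dose: 85 + 28 = Day 113.

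**Where it does not fit.** In 5.6.2, exposure = (day of last dose − 1) + 28.

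| Last dose | On schedule | Exposure (days) | Highest row met | Window for last dose | Range of exposure |
|---|---|---|---|---|---|
| 1st | Day 1 | 28 | ≥1 | none | 28 |
| 2nd | Day 29 | 56 | ≥29 | Days 22 to 36 | 49 to 63 |
| 3rd | Day 57 | 84 | ≥57 | Days 50 to 64 | 77 to 91 |
| 4th | Day 85 | 112 | ≥85 | Days 78 to 92 | 105 to 119 |

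"Highest row met" refers to the on-schedule patient.

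**Top row.** 112 = 16 × 7, so on-schedule treatment gives exactly 16 weeks, and 112 < 113. Reaching 113 needs (d − 1) + 28 ≥ 113, so d ≥ 86. Within the window, that means a week 12 dose on Days 86 to 92.

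**With the cut at ≥112.** The condition becomes d ≥ 85, so Days 85 to 92 qualify. Patients last dosed on Days 78 to 84 (105 to 111 days) still fall below the row.

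**Lower rows.**
- ≥29: a single-dose patient always has 28 days. The earliest in-window second dose, Day 22, gives (22 − 1) + 28 = 49. The row therefore separates single-dose patients from everyone with a later in-window dose. A cut at ≥28 would be met by every treated patient, just as ≥1 is.
- ≥57: among patients whose last dose was the second, it needs Days 30 to 36. At ≥56 it needs Days 29 to 36.
- ≥85: among patients whose last dose was the third, it needs Days 58 to 64. At ≥84 it needs Days 57 to 64.
- In each of these two rows, the present cut sets apart the 7 late days of the 15 permitted, and the lower cut would set apart the 7 early days. The split by timing moves but does not shrink.

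**Duration is not dose count.** Doses on Days 1 and 85 alone give (85 − 1) + 28 = 112 days from two injections.

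**The case against.** The strongest reply is that the SAP gives the rows no meaning. Read as plain thresholds, the present rows keep on-schedule patients with different dose counts apart: 28 days meets only ≥1, 56 meets ≥29, 84 meets ≥57 and 112 meets ≥85. On that reading nothing is miscounted. The idea that the cut-points were carried over from the visit schedule is an inference. The exact match and the reuse of the same values in 5.6.3 support it, but the documents do not state it.

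Much of this stands. A reader might infer that all four cut-points are off by one and should all be lowered. The documents do not support that. No text pairs a given row with a given number of doses, lowering ≥29 would destroy the one row that is independent of dose timing, and lowering ≥57 and ≥85 only exchanges late dosers for early ones.

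The reply does not rescue the top row. If the first four rows mark entry into successive dosing intervals, ≥113 would mark a fifth interval in a four-dose regimen. Within the permitted window, only a late week 12 dose can meet it. Changing it to ≥112 also moves a timing split from late to early dosers, but it puts the patient treated exactly to plan into the row and makes the row equal 16 weeks.

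A reader might also infer that completion or safety rates are misreported. They are not. Treatment completion is reported under 5.5.2 and injection counts under 5.6.1, and incidence rates divide by the observation period (4.5.1).

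**Conclusion.** The point holds for the top row and is minor. Followed exactly, SAP 5.6.2 excludes from ≥113 days every patient whose four doses were given on Days 1, 29, 57 and 85, and within the dosing window it admits only those whose week 12 dose was 1 to 7 days after target. This rests on the first dose being Day 1 and on doses given inside the ±7-day window. It does not depend on how the cut-points came about.

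The number of patients affected is not in the documents. Dosing was stopped with 63 patients randomized, how many had a week 12 dose is not stated, and the number affected could be zero. The mean, SD, median, quartiles, minimum and maximum of exposure do not use the rows. The lower rows are not shown to be wrong.

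**What to change.** - Keep the + 28 formula, which agrees with the protocol, and change ≥113 to ≥112 days.
- Keep ≥29.
- Add one sentence to 5.6.2 saying that the rows describe duration and not the number of doses received, and referring to the injection counts in 5.6.1.
- Optional: change ≥57 and ≥85 to ≥56 and ≥84, so that on-schedule patients with two or three doses reach those rows. The price is that early dosers are then split off in place of late ones, and on-schedule three-dose patients (84 days) would share the 84 to 111 band with early four-dose patients (105 to 111 days).

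The cost is one cut-point and one sentence, or three cut-points with the optional change. No protocol amendment is needed, because protocol 10.4.4.3 leaves the time periods to the SAP. Exposure summary statistics, incidence rates, injection counts and disposition are unchanged. Changing the formula to + 29 would also make the present rows fit, but it would depart from the protocol.
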